5.3.2 Eliciting Adverse Event Information

A consistent methodology of non-directive questioning should be adopted for eliciting adverse event information at all subject evaluation time-points. Examples of non-directive questions include the following:

“How have you felt since your last clinic visit?”

“Have you had any new or changed health problems since you were last here?”

5.3.3 Assessment of Severity of Adverse Events

Table 4 provides guidance for assessing adverse event severity.

Table 4 Adverse Event Severity Grading Scale

Severity	Description
Mild	Discomfort noticed, but no disruption of normal daily activity
Moderate	Discomfort sufficient to reduce or affect normal daily activity
Severe	Incapacitating with inability to work or to perform normal daily activity

Note: Regardless of severity, some events may also meet seriousness criteria. Refer to definition of a serious adverse event (see Section 5.1.2).

5.3.4 Assessment of Causality of Adverse Events

Investigators should use their knowledge of the subject, the circumstances surrounding the event, and an evaluation of any potential alternative causes to determine whether or not an adverse event is considered to be related to the study drug, indicating "yes" or "no" accordingly. The following guidance should be taken into consideration:

- Temporal relationship of event onset to the initiation of study drug
- Course of the event, considering especially the effects of dose reduction, discontinuation of study drug, or re-introduction of study drug (where applicable)
- Known association of the event with the study drug or with similar treatments
- Known association of the event with the disease under study
- Presence of risk factors in the Subject or use of concomitant medications known to increase the occurrence of the event
- Presence of non-treatment-related factors that are known to be associated with the occurrence of the event

For subject receiving combination therapy, causality will be assessed individually for each protocol-mandated therapy.

5.3.5 Procedures for Recording Adverse Events

Investigators should use correct medical terminology/concepts when recording adverse events on the Adverse Event eCRF. Avoid colloquialisms and abbreviations.

Only one adverse event term should be recorded in the event field on the Adverse Event eCRF.

5.3.5.1 Diagnosis versus Signs and Symptoms

For adverse events, a diagnosis (if known) should be recorded on the Adverse Event eCRF rather than individual signs and symptoms (e.g., record only liver failure or hepatitis rather than jaundice, asterixis, and elevated transaminases). However, if a constellation of signs and/or symptoms cannot be medically characterized as a single diagnosis or syndrome at the time of reporting, each individual event should be recorded

on the Adverse Event eCRF. If a diagnosis is subsequently established, all previously reported adverse events based on signs and symptoms should be nullified and replaced by one adverse event report based on the single diagnosis, with a starting date that corresponds to the starting date of the first symptom of the eventual diagnosis.

5.3.5.2 Adverse Events Occurring Secondary to Other Events

In general, adverse events occurring secondary to other events (e.g., cascade events or clinical sequelae) should be identified by their primary cause, with the exception of severe or serious secondary events. However, medically significant adverse events occurring secondary to an initiating event that are separated in time should be recorded as independent events on the Adverse Event eCRF. For example:

- If vomiting results in mild dehydration with no additional treatment in a healthy adult, only vomiting should be reported on the eCRF.
- If vomiting results in severe dehydration, both events should be reported separately on the eCRF.
- If a severe gastrointestinal hemorrhage leads to renal failure, both events should be reported separately on the eCRF.
- If dizziness leads to a fall and subsequent fracture, all three events should be reported separately on the eCRF.

All adverse events should be recorded separately on the Adverse Event eCRF if it is unclear as to whether the events are associated.

5.3.5.3 Persistent or Recurrent Adverse Events

A persistent adverse event is one that extends continuously, without resolution, between subject evaluation time-points. Such events should only be recorded once on the Adverse Event eCRF. The initial severity of the event should be recorded, and the severity should be updated to reflect the most extreme severity any time the event worsens. If the event becomes serious, the Adverse Event eCRF should be updated to reflect this.

A recurrent adverse event is one that resolves between subject evaluation time-points and subsequently recurs. Each recurrence of an adverse event should be recorded separately on the Adverse Event eCRF.

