3.1.5 Open-Label Extension

Subjects who complete the double-blind 24-week treatment period will be able to participate in an optional 52-week OLE period where they will receive open-label balovaptan treatment.

Participation in the OLE will also be permitted for all subjects who have completed treatment to Week 24, prior to implementation of the OLE. Furthermore, individuals who participated in the PK cohort and were required to stop dosing before week 8, and then did not participate further in BP30153, will be allowed to participate in the OLE (see *Section 4.2.4* for detailed eligibility criteria). All subjects meeting these requirements will need to be re-consented for participation in the OLE after meeting requirements specified in [Appendix 11](#).

Subjects who do not want to participate in the OLE will complete the follow-up visits as detailed in the Schedule of Assessments (see [Appendix 1](#)). Subject treatment allocation during the blinded treatment period will not be unblinded until all patients have completed the double-blind period.

During the OLE portion of the study, all subjects will be provided with 10 mg *eq* balovaptan irrespective of previous treatment allocation.

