5.1.1 Adverse Events

According to the ICH guideline for Good Clinical Practice, an adverse event is any untoward medical occurrence in a clinical investigation subject administered a pharmaceutical product, regardless of causal attribution. An adverse event can therefore be any of the following:

- Any unfavorable and unintended sign (including an abnormal laboratory finding), symptom, or disease temporally associated with the use of a medicinal product, whether or not considered related to the medicinal product.
- Any new disease or exacerbation of an existing disease (a worsening in the character, frequency, or severity of a known condition), except as described in Section [5.3.5.8](#).
- Recurrence of an intermittent medical condition (e.g., headache) not present at baseline.
- Any deterioration in a laboratory value or other clinical test (e.g., ECG, X-ray) that is associated with symptoms or leads to a change in study treatment or concomitant treatment or discontinuation from study drug.
- Adverse events that are related to a protocol-mandated intervention, including those that occur prior to assignment of study treatment (e.g., screening invasive procedures such as biopsies).

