5.3.5.4 Abnormal Laboratory Values

Not every laboratory abnormality qualifies as an adverse event. A laboratory test result should be reported as an adverse event if it meets any of the following criteria:

- Accompanied by clinical symptoms
- Results in a change in study treatment (e.g., dosage modification, treatment interruption, or treatment discontinuation)

- Results in a medical intervention (e.g., potassium supplementation for hypokalemia) or a change in concomitant therapy
- Clinically significant in the Investigator's judgment

It is the Investigator's responsibility to review all laboratory findings. Medical and scientific judgment should be exercised in deciding whether an isolated laboratory abnormality should be classified as an adverse event.

If a clinically significant laboratory abnormality is a sign of a disease or syndrome (e.g., alkaline phosphatase and bilirubin 5 times the upper limit of normal (ULN) associated with cholecystitis), only the diagnosis (i.e., cholecystitis) should be recorded on the Adverse Event eCRF.

If a clinically significant laboratory abnormality is not a sign of a disease or syndrome, the abnormality itself should be recorded on the Adverse Event eCRF, along with a descriptor indicating if the test result is above or below the normal range (e.g., "elevated potassium", as opposed to "abnormal potassium"). If the laboratory abnormality can be characterized by a precise clinical term per standard definitions, the clinical term should be recorded as the adverse event. For example, an elevated serum potassium level of 7.0 mEq/L should be recorded as "hyperkalemia".

Observations of the same clinically significant laboratory abnormality from visit to visit should not be repeatedly recorded on the Adverse Event eCRF, unless the etiology changes. The initial severity of the event should be recorded, and the severity or seriousness should be updated any time the event worsens.

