### **2.4 ANALYSIS TIMING**

The primary analysis will be conducted when the double-blind 24-week treatment period ends. Database lock will occur once all subjects have either completed the 24-week assessment or withdrawn from the study early, and all data required for analysis have been cleaned and verified.

An efficacy and safety interim analysis is planned once approximately 80 subjects taking either balovaptan 10 mg equivalent or placebo (i.e., approximately 40 subjects per treatment arm) have completed their 12-week visit without dose interruptions or adjustments to allow internal decisions for the next steps of the development plan.

Given the hypothesis generating nature of this study, the Sponsor may conduct up to two interim analyses beyond what is specified elsewhere in this protocol. The decision to conduct such an interim analysis and its timing will be documented in the Sponsor's study master file prior to the conduct of the interim analysis. The clinical study report will also document that such an interim analysis occurred. Interim analyses will be performed and interpreted by the IMC and SOC members (as appropriate), who will have full access to unblinded data.

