### **4.6 SAFETY ANALYSES**

Summary tables and graphs will be provided both for the “Safety Global” and for the “Safety Inferential” populations, while listings of individual data will be provided for the “Safety Global” population only, separately by subjects’ patterns (a, b, c, d).

As appropriate, listings, summary tables and graphs by treatment group will be provided for safety and tolerability assessments, including:

- Incidence of adverse events (overall, by intensity, and by relationship to study medication).

- Serious adverse events and adverse events of special interest will be reported separately.
- [REDACTED]
- Vital signs (systolic blood pressure, diastolic blood pressure, pulse rate, and orthostatic effects)
- [REDACTED]
- Physical examination (height, weight, neurological examination)
- Safety laboratory values (including hematology, blood chemistry, coagulation, and urinalysis parameters)
- Incidence of marked laboratory abnormalities
- Clinical assessment of suicidality (C-SSRS)

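### Severity, seriousness and relationship of an adverse event that began double-blind can carry an open-label rating into the double-blind safety tables, placebo included, because no cut-off is set at the first open-label dose

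*Protocol*

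**What the plan says.** **Recording.** Protocol 5.3.5.3 says of a persistent event: "Such events should only be recorded once on the Adverse Event eCRF". It continues "The initial severity of the event should be recorded", and then "the severity should be updated to reflect the most extreme severity any time the event worsens". If the event becomes serious, the same record is updated. Protocol 5.3.5.4 applies the rule to laboratory abnormalities ("the severity or seriousness should be updated any time the event worsens"), and 5.3.5.5 does so for vital signs. Those two sections allow a fresh entry where the cause of the abnormality has changed; 5.3.5.3 has no such exception.

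**Treatment.** Protocol 3.1.5 gives every subject in the extension 10 mg eq "balovaptan irrespective of previous treatment allocation". Under 4.2.4, subjects move straight into the extension where possible, and only adverse events that the investigator judges prohibitive keep a subject out. Under 5.3.1, adverse events are collected without a break from the first dose until 6 weeks after the last.

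**Analysis.** SAP 1 covers the double-blind 24-week period and leaves the extension to a separate document. SAP 2.4 says "Database lock will occur once all subjects have either completed the 24-week assessment or withdrawn from the study early". SAP 4.6 lists "Incidence of adverse events (overall, by intensity, and by relationship to study medication", and serious events are summarized separately.

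**The concern.** A persistent event is one record with one onset date, and its severity and seriousness follow the event through a change of treatment. If the event starts in the double-blind period, its onset places it there. If it worsens after the first open-label dose and before the data are extracted, the record can then show a double-blind onset with an open-label severity.

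The placebo column matters most. Former placebo subjects are newly exposed at Week 24. If the drug aggravates an event that is already present, that harm would appear under placebo and narrow the severe-event or serious-event difference. Ratings in the active arm can also rise, so the net direction is not known. In addition, the later rating is made when the site knows that the subject is taking balovaptan, so an open-label judgement could stand in a table meant to rest on blinded ones.

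Only the tables by severity, seriousness and relationship are exposed. An event with double-blind onset belongs in the overall incidence table whatever happens to it later.

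**Working it through.** The plan states no figure on this point, so the check sets the texts side by side and then gives an illustration on assumed rates.

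**Step 1. Can an event be open when treatment changes?** Yes. Rollover is direct where possible, and non-prohibitive events do not bar entry (Protocol 4.2.4). A pre-existing condition is defined by presence at study screening (5.3.5.8), so entering the extension directly does not restart an ongoing event as a new one.

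**Step 2. How long can the record be raised?** Up to 76 weeks of treatment plus 6 weeks of follow-up: 76 + 6 = 82 weeks, against a 24-week double-blind period (82 / 24 = 3.4 times as long). For the double-blind tables, only changes made before extraction count.

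**Step 3. Can open-label changes precede the lock?** Yes. The lock waits for the last subject's Week 24 or withdrawal. Recruitment began in November 2016 (Protocol 1.2.2.1), and SAP 4.5.2 refers to randomizations up to 21 February 2019, so Week 24 dates are widely spread. Early completers can be well into the 52-week extension at lock; the last subjects will have little or no open-label time.

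**Step 4. Does the SAP separate the periods for adverse events?** No.

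| Item | SAP rule | Cut at the extension? |
|---|---|---|
| Week 24 visit window (3.3) | Closes before screening for the extension | Yes |
| Main Part safety dataset (4.1) | Defined by subjects and maximum treatment duration | No date rule for events |
| Adverse event tables (4.6) | Events recorded over the study period, by severity and relationship; serious events separately | No |

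The SAP gives no treatment-emergent definition and does not say which severity value the tables use. Visit-based data are protected; the ratings on an adverse event record are not. SAP 1 applies the same rules to interim analyses as appropriate, and the planned interim uses the Safety Inferential population (4.5.2), so the gap exists there too.

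**Step 5. Relationship.** Protocol 5.3.5.3 names severity and seriousness only. Relationship is exposed less directly: there is one record, and Protocol 5.4 foresees causality changing on new information for events reported immediately.

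**Step 6. Illustration.** The target of 80 evaluable subjects per arm at Week 24 comes from Protocol 6.1. Both rates below are assumptions.

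Subjects with a raised rating per arm = 80 × (proportion with an event ongoing at rollover) × (proportion of those worsening on open-label drug before extraction).

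| Ongoing at rollover | 2% worsen | 5% | 10% | 20% |
|---|---|---|---|---|
| 5% | 0.08 | 0.2 | 0.4 | 0.8 |
| 10% | 0.16 | 0.4 | 0.8 | 1.6 |
| 20% | 0.32 | 0.8 | 1.6 | 3.2 |
| 30% | 0.48 | 1.2 | 2.4 | 4.8 |

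The range is 0.08 / 80 = 0.1% to 4.8 / 80 = 6.0% of an arm. The formula takes all 80 as entering the extension, which is optional, so at any given pair of rates the count is an upper figure. It counts any rise in rating, not only rises to severe or serious.

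**The case against.** The strongest case against is that this is a silence in the SAP, not an instruction to miscount. The SAP confines itself to the double-blind period, and a programmer could reasonably cut the data at the first open-label dose without being told. That stands in part: a reader might infer that open-label worsening *is* counted in the double-blind arm, and no text says so. It *can* be, because the recording rule is explicit and nothing in the SAP undoes it.

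Other stronger readings are tempting but unsupported:

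- **That the earlier value is overwritten and lost.** The initial severity must be recorded, and Protocol 7.2 keeps an audit trail of entries and changes with dates. The documents do not show whether the eCRF has separate fields for initial and most extreme severity. What remains is that the SAP names neither source for its tables.
- **That no exception exists.** For laboratory and vital-sign events, a change of cause permits a new entry, and worsening due to newly started balovaptan could qualify. Protocol 5.3.5.2 also separates severe or serious secondary events, but that concerns a different event, not the same one getting worse. Other persistent events have no exception.
- **That the rule conflicts with Protocol 5.1.1.** That section defines what an adverse event is; 5.3.5.3 says how a continuing one is entered. The two are compatible.
- **That the extension report loses the event.** Its methods are in a separate document that is not available here.
- **That the severe-event rate rises by a definite amount.** With 15% to 30% ongoing and 5% to 10% worsening, 0.6 to 2.4 subjects are affected, which is 0.75 to 3.0 points on 80. Adding this to the severe rate would require every worsening to reach severe, in subjects with no other severe event, all before lock and with full entry to the extension. Likewise, any stated bias between the arms would come only from assuming different worsening rates in each.

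**Conclusion.** The point holds as a gap in attribution. Followed as written, the recording rule, the switch to open-label drug, the late lock and the absence of an adverse event cut-off together allow an open-label rating into the double-blind severity, seriousness and relationship tables, including under placebo. Overall incidence and the efficacy analyses are not affected.

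The size is unknown and probably small. It depends on how many subjects roll over with an event ongoing, how many of those worsen before extraction, and which severity value the tables use; the documents give none of these. Even so, if severe and serious events are few at about 80 subjects per arm, one or two misplaced subjects could change how a comparison reads. The repair is cheap and should be made before lock.

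**What to change.** 1. **SAP 4.6.** Add a rule that, in the double-blind tables, an event's severity, seriousness and relationship are the worst values reached before the subject's first open-label dose. Subjects who do not enter the extension are unaffected. Apply the rule to any interim analysis.
2. **eCRF guidance for Protocol 5.3.5.3 to 5.3.5.5.** For an event ongoing at the first open-label dose, capture the date of any later worsening or change to serious, either as a dated change on the record or as a new entry. Immediate reporting to the sponsor stays as it is.
3. **Records already updated.** Use the audit trail to recover the value in force before the first open-label dose, and query the site where entry dates do not settle when the worsening occurred.

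The cost is one SAP rule, a short addition to the guidance and some queries. If new entries are used, a few events will be shown in both periods, which a table footnote can explain.

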5.3.5.4 Abnormal Laboratory Values

Not every laboratory abnormality qualifies as an adverse event. A laboratory test result should be reported as an adverse event if it meets any of the following criteria:

- Accompanied by clinical symptoms
- Results in a change in study treatment (e.g., dosage modification, treatment interruption, or treatment discontinuation)

- Results in a medical intervention (e.g., potassium supplementation for hypokalemia) or a change in concomitant therapy
- Clinically significant in the Investigator's judgment

It is the Investigator's responsibility to review all laboratory findings. Medical and scientific judgment should be exercised in deciding whether an isolated laboratory abnormality should be classified as an adverse event.

If a clinically significant laboratory abnormality is a sign of a disease or syndrome (e.g., alkaline phosphatase and bilirubin 5 times the upper limit of normal (ULN) associated with cholecystitis), only the diagnosis (i.e., cholecystitis) should be recorded on the Adverse Event eCRF.

If a clinically significant laboratory abnormality is not a sign of a disease or syndrome, the abnormality itself should be recorded on the Adverse Event eCRF, along with a descriptor indicating if the test result is above or below the normal range (e.g., "elevated potassium", as opposed to "abnormal potassium"). If the laboratory abnormality can be characterized by a precise clinical term per standard definitions, the clinical term should be recorded as the adverse event. For example, an elevated serum potassium level of 7.0 mEq/L should be recorded as "hyperkalemia".

Observations of the same clinically significant laboratory abnormality from visit to visit should not be repeatedly recorded on the Adverse Event eCRF, unless the etiology changes. The initial severity of the event should be recorded, and the severity or seriousness should be updated any time the event worsens.

5.3.5.5 Abnormal Vital Sign Values

Not every vital sign abnormality qualifies as an adverse event. A vital sign result should be reported as an adverse event if it meets any of the following criteria:

- Accompanied by clinical symptoms
- Results in a change in study treatment (e.g., dosage modification, treatment interruption, or treatment discontinuation)
- Results in a medical intervention or a change in concomitant therapy
- Clinically significant in the Investigator's judgment

It is the Investigator's responsibility to review all vital sign findings. Medical and scientific judgment should be exercised in deciding whether an isolated vital sign abnormality should be classified as an adverse event.

If a clinically significant vital sign abnormality is a sign of a disease or syndrome (e.g., high blood pressure), only the diagnosis (i.e., hypertension) should be recorded on the Adverse Event eCRF.

Observations of the same clinically significant vital sign abnormality from visit to visit should not be repeatedly recorded on the Adverse Event eCRF, unless the etiology changes. The initial severity of the event should be recorded, and the severity or seriousness should be updated any time the event worsens.

